3 (Persistent grade 2: Consider similar dose adjustments if persistent and not responding to optimal management in the opinion of PI and treating physician)	1st time	Hold venetoclax and/or quizartinib. Resume venetoclax and/or quizartinib at prior dose if recovery to ≤ Grade 1 or baseline occurs within 14 days. If toxicity persists for 15-28 days, hold therapy and resume at ONE dose level below current dose for venetoclax OR quizartinib OR both based on which medication is likely causing the toxicity ONLY after recovery of toxicity to ≤ Grade 2. Dose re-escalation to prior dose of venetoclax OR quizartinib OR both is permitted if tolerated and no recurrent Grade 3 or 4 toxicities occur over 4 weeks while on the lower dose level.
	2nd time	Hold venetoclax and/or quizartinib. Follow until toxicity ≤ Grade 2. Resume at TWO dose level below current dose for venetoclax OR quizartinib OR both based on which medication is likely causing the toxicity ONLY after recovery of toxicity to ≤ Grade 2. Dose re-escalation by one dose level every 4 weeks of venetoclax OR quizartinib OR both is permitted if tolerated and no recurrent Grade 3 or 4 toxicities occur over the 4 weeks while on the lower dose level.

	3rd time	Stop venetoclax and quizartinib and discontinue patient. (For patients with clinical benefit/response from the combination we will consider continuation if toxicities resolve to ≤ grade 1 within 28 days and with proper dose adjustments after consultation with the PI and the sponsor.)
4	1st time	Hold venetoclax and/or quizartinib. Resume venetoclax and/or quizartinib at prior dose if recovery to ≤ Grade 1 or baseline occurs within 14 days. If toxicity persists for 15-28 days, hold therapy and resume at ONE dose level below current dose for venetoclax OR quizartinib OR both based on which medication is likely causing the toxicity ONLY after recovery of toxicity to ≤ Grade 2. Dose re-escalation to prior dose of venetoclax OR quizartinib OR both is permitted if tolerated and no recurrent Grade 3 or 4 toxicities occur over 4 weeks while on the lower dose level.
	2 nd time	Stop venetoclax and quizartinib and discontinue patient. (For patients with clinical benefit/response from the combination we will consider continuation if toxicities resolve to ≤ grade 1 within 28 days and with proper dose adjustments after consultation with the PI and the sponsor.)

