Cardiac Toxicity	Grade 1 QTc ≥ 450 and ≤ 480 msec	Check magnesium and potassium levels and correct any abnormalities. If possible, stop any medications that may prolong the QTc interval. Continue quizartinib at the same dose.
Cardiac Toxicity	Grade 2 QTc > 480 and ≤ 500 msec	Check magnesium and potassium levels and correct any abnormalities. If possible, stop any medications that may prolong the QTc interval. The dose of quizartinib will be reduced one level without interruption of dosing. Following dose reduction, the quizartinib dose may be resumed at the previous level in the next cycle if the QTc has decreased to within 30 msec of baseline or <450 msec but subject must be monitored closely for QT prolongation for the first cycle at the increased dose. Subjects who experience >480 msec QTc prolongation and undergo dose interruption and/or reduction must be monitored closely with ECGs, performed twice weekly for the first week of the QTc prolongation and then weekly thereafter until the QTc prolongation is resolved.

Cardiac Toxicity	Grade 3 QTc interval >500 msec (at least on two separate EKGs) or >60 ms change from baseline	Check magnesium and potassium levels and correct any abnormalities. Interrupt quizartinib and if possible any medications that may prolong the QTc interval. Quizartinib dosing will be interrupted for up to 14 days. If QTcF returns to within 30 msec of baseline or <450 msec within 14 days, quizartinib administration may be resumed at a reduced dose (reduce by one level). Subjects who experience >500 msec QTcF prolongation and undergo dose interruption and/or reduction must be monitored closely with ECGs, performed twice weekly for the first week of the QTcF prolongation and then weekly thereafter until the QTc prolongation is resolved.
Cardiac Toxicity	Grade 4 , and Torsade de pointes or polymorphic ventricular tachycardia or signs/symptoms of serious arrhythmia (i.e., grade 4)	Quizartinib dosing will be permanently discontinued

- If the criteria to resume treatment are met, the subject should restart treatment at the next scheduled time point per protocol. However, if the treatment is delayed past the next scheduled time point per protocol, the next scheduled time point will be delayed until dosing resumes.

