5.2.3 Intra-patient dose escalation

Intra-patient dose escalation of venetoclax and quizartinib (in accordance with the dosing schema in Table 1) will be permitted provided:

- Patient has completed ≥ 1 cycle at their current dose level
- Patient has not experienced any grade 3 or higher non-hematologic drug-related toxicity (including Grade 3 QTcF prolongation), and
- Patient has not experienced hematologic DLT, and
- At least 6 patients have been treated at the next higher dose level and followed for at least 28 days without experiencing DLT and this dose level has been deemed safe and does not exceed the RP2D.
- The dose may be escalated by one dose level per cycle (per Table 1) provided such dose level does not exceed RP2D.
- Dose escalation of only one of the two agents is allowed if judged in the best interest of the patient (e.g., in patients with neutropenia this would be likely secondary to venetoclax, in patients with QTc changes this would be likely secondary to quizartinib).
- However, the dose of any agent cannot be escalated beyond the established RP2D for the combination.

5.2.4 Modifications of dose schedules other than the above will be allowed within the following guidelines:

5.2.4.1 Further dose reductions can be made to keep clinically significant toxicities grade ≤ 2 .

5.2.4.2 Dose adjustments by more than 1 dose level at a time (e.g., from quizartinib 60 mg daily to 20 mg daily) can be considered when judged in the best interest of the patient (e.g. severe myelosuppression or other toxicity attributable to one of the agents) when toxicity has resolved. The reason for this reduction will be discussed with the PI or Co-PI and documented in the medical record.

5.2.4.3 A patient who has had a dose reduction because of any of the reasons mentioned above may have their dose escalated provided the patient has remained free of toxicity requiring dose adjustments as defined above for at least 1 month. Escalation will be made by 1 dose-level increment only, and not more frequent than every month.

5.2.4.4 Treatment interruptions and dose modifications other than the ones mentioned above can be considered after discussion with the PI and proper documentation of the rationale. Dose adjustment/delay of only one of the agents is permissible if the toxicity is most likely judged to be related to one of the agents by the investigator (e.g., in patients with

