- 7.2.8 EKG will be performed on day 1, day 5, day 8, and day 12 of the first cycle (all ± 2 days) Day 1 and day 8 ECG are collected pre-dose; day 5 are collected pre-dose and 4 hrs (+/- 2 hrs) post-dose; day 12 are collected 4 hrs (+/- 2 hrs) post-dose. Then ECG to be done on day 1 of each cycle for cycles 2, 3, 4 and 5 before initiation of quizartinib and 4 hr (+/- 2 hrs) post dose, then pre-dose every 2 subsequent cycles. EKG may be omitted if patient has not received study drug (quizartinib) in the 48 hrs preceding the time when EKG is done. EKG at screening and for the first 3 cycles will be done in triplicate. Subjects **should rest in the supine position or semi-recumbent, with the same position used for an individual subject for the duration of the study, for at least 5 minutes before each 12-lead ECG recording is started. The ECGs should be reviewed, signed,**

and dated by a qualified physician (or qualified physician's assistant or nurse practitioner) and any clinically important finding recorded on the appropriate eCRF. The results will include heart rate, PR interval, QRS interval, QT interval, and QTcF interval. QTcF is calculated using the formula, $(QT)/3\sqrt{RR}$. All screening and on study ECGs should be obtained in triplicate (10 seconds for each ECG over the 5-minute period).

- A. On patients who increase the dose of Quizartinib or start therapy with a drug that is a moderate CYP3A4 inhibitor, an EKG will be required 24 hrs (± 6 hrs), 7 days (± 2 days) and 14 days (± 2 days) after the dose increase or after the start of the moderate CYP3A4 inhibitor.
- B. Patients who had their dose reduced because of QTc prolongation and have their dose re-escalated as described in section 5.2.3 will have an EKG repeated 24 hrs (± 6 hrs) and 7 days (± 2 days) after re-escalation.
- C. The QTc interval will be calculated by Fridericia's correction factor (QTcF). The 12-lead EKG evaluation will consist of 3 separate EKGs obtained at least 5 minutes apart.

7.2.9 Peripheral blood (up to 40 cc each time) and bone marrow (up to 15 cc each time) for pharmacodynamic studies (Optional) as defined in section 6.0 on

Peripheral blood:

- Prior to first dose of quizartinib at baseline (Cycle 1 Day 1).
- Cycle 1 Day 8: prior to the first dose of venetoclax
- Cycle 1 Day 15: prior to the dose of quizartinib and venetoclax (steady state)
- Cycle 1 Day 28 (+/- 4 days): prior to the dose of quizartinib and venetoclax
- At progression/relapse (if sample available)

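### Sections 5.2.3, 5.2.4.3, Table 2 and 7.2.8 conflict on raising quizartinib again after a QTc-related reduction, and two ECG lists are left unreconciled

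*Combined protocol and SAP*

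**What the plan says.** Raising quizartinib again after a QTc-related reduction is touched on in five places.

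- **Section 5.2.3** (intra-patient dose escalation) sets conditions that include "Patient has not experienced any grade 3 or higher non-hematologic drug-related toxicity (including Grade 3 QTcF prolongation), and" and "Patient has completed ≥ 1 cycle at their current dose level". It also requires that six patients have already been followed for 28 days one level up, and it caps the dose at the RP2D.
- **Section 5.2.4.3**: "A patient who has had a dose reduction because of any of the reasons mentioned above may have their dose escalated", on condition of at least one month without toxicity that would call for a dose change. Steps are one level at a time and no more often than monthly.
- **Section 5.2.2, Table 2, row "Grade 2 QTc > 480 and ≤ 500 msec"**: the dose drops one level without a break, after which "the quizartinib dose may be resumed at the previous level in the next cycle". The condition is a QTc below 450 msec or no more than 30 msec from baseline, with close QT monitoring through the first cycle at the higher dose.
- **Section 5.2.2, Table 2, Grade 3 QTc row** (above 500 msec on two ECGs, or a rise of more than 60 ms): interrupt for up to 14 days and, on recovery, resume one level lower. Nothing is said about a later return to the former level.
- **Section 7.2.8** has two ECG lists. Item B addresses "Patients who had their dose reduced because of QTc prolongation and have their dose re-escalated as described in section 5.2.3" and gives 24 hours and 7 days. Item A addresses "On patients who increase the dose of Quizartinib or start therapy with a drug that is a moderate CYP3A4 inhibitor" and gives 24 hours, 7 days and 14 days.

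No passage says which of these prevails.

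**The concern.** Section 2.2 names QTc prolongation above 500 msec as the dose-limiting toxicity of quizartinib, so the rule for going back up after such an event should be unambiguous. Here two patients with the same event could be handled differently, each in line with a passage of the protocol. What is at stake is patient safety and the consistency of dose received. The trial reads out safety and response at a chosen RP2D. If some patients return to a former level while others with the same history stay lower, dose exposure and later QTc events partly reflect which passage was followed.

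**Working it through.** This is mainly a comparison of text; the only arithmetic concerns timing and the overlap of two QTc ranges.

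**1. Grade 3 QTcF.** There are two ways to read 5.2.3.
- If it governs re-escalation, as 7.2.8 B says, the patient is barred by 5.2.3 but allowed by 5.2.4.3 after a month. The Grade 3 QTc row does not decide between them.
- If it covers only a move to a higher cohort level, 5.2.4.3 is left as the rule, and 7.2.8 B points to the wrong section.

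Either reading leaves something to correct.

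**2. Grade 2 QTc: timing.** Inputs are cycle 1 ECGs on Days 5, 8 and 12 (7.2.8), a cycle of 28 ± 7 days (5.1), and an earliest restart at Day 21 for active disease, not allowed in phase Ib cycle 1 (5.1.1.1). For a reduction on day d of a cycle of length L, days to the next Day 1 = L + 1 − d.

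| Reduction on | L = 21 | L = 28 | L = 35 |
|---|---|---|---|
| Day 5 | 17 | 24 | 31 |
| Day 8 | 14 | 21 | 28 |
| Day 12 | 10 | 17 | 24 |

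With the standard 28-day cycle, all three intervals are under a month, so Table 2 can permit what 5.2.4.3 does not yet permit. Only a cycle stretched to 35 days brings the Day 5 case to a month. These are the earliest dates under Table 2, because QTc must first recover. If a completed cycle in 5.2.3 means a whole 28-day cycle begun at the reduced level (an assumption), its wait is 24 + 28 = 52, 21 + 28 = 49 or 17 + 28 = 45 days.

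**3. Where all three outcomes meet.** The Grade 2 row covers QTc above 480 and up to 500 msec; the Grade 3 row also admits a rise above 60 ms. Both apply when baseline is below QTc − 60:
- at QTc 481, baseline below 481 − 60 = 421 msec;
- at QTc 500, baseline below 500 − 60 = 440 msec.

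Both lie within the entry limit of 450 msec (section 4.2). If 5.2.3 uses the Table 2 definition of Grade 3, such a patient may return next cycle (Grade 2 row), is barred (5.2.3), and may return after a month (5.2.4.3).

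**4. ECGs after the increase.** A has three time points and B two; the difference is the 14-day ECG. Section 2.2 gives a half-life of about 100 hours. Assuming simple first-order accumulation, the share of the way to the new steady state is 1 − 2^(−168/100) ≈ 69% at 7 days and 1 − 2^(−336/100) ≈ 90% at 14 days. The two lists are therefore not interchangeable. This does not say which list is right.

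**The case against.** The best defence is that 5.2.3 was never a re-escalation rule. Its condition on six patients one level up fits a phase Ib patient moving up a cohort level, and sections 3.5 and 11.1 cite it for exactly that. Section 5.2.4 is introduced as covering changes not dealt with before it, so the specific Grade 2 row could be taken to govern. The trial is run at one institution, Table 2 is offered as guidance, and cases can be discussed with the PI.

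Much of this stands, but it does not clear the text. On that reading the reference in 7.2.8 B is wrong. Section 5.2.4.3 still reaches back to reductions for reasons given earlier, so the Grade 2 timing conflict remains. PI discussion makes divergent handling less likely but sets no order of precedence.

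Four stronger inferences are tempting and are not supported:
- **That any one patient faces all three outcomes.** A plain Grade 2 patient is not caught by the Grade 3 bar, and a plain Grade 3 patient has no next-cycle allowance. All three meet only in narrow cases: the overlap in step 3, or a Grade 2 QTc patient with another earlier Grade 3 drug-related non-hematologic toxicity.
- **That patients with known QTc sensitivity get fewer ECGs.** Item A is worded for any quizartinib increase, and B does not exempt them from it. Table 2 also asks for close monitoring after a Grade 2 return, and Day 1 ECGs continue in cycles 2 to 5. The fault is that the relation between A and B is unstated.
- **That the general Grade 3 row adds a competing rule.** Its sentence "Dose re-escalation to prior dose of venetoclax OR quizartinib OR both is permitted if tolerated" follows the branch for toxicity lasting 15 to 28 days. QTc has its own rows, and the Grade 3 one requires recovery within 14 days.
- **That the number affected can be read from section 2.2.** The 19% with a change above 60 msec at 60 mg is a monotherapy rate of maximum change. It does not count patients who recover, resume and are then considered for re-escalation.

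**Conclusion.** The passages conflict and should be reconciled. Grade 3 QTcF patients are barred or allowed after a month, unless 5.2.3 is limited to cohort escalation, in which case the cross-reference is wrong. Grade 2 patients may return from the next cycle or must wait a month or a completed cycle. With a 28-day cycle and a Day 5 to Day 12 reduction, next-cycle return means 17 to 24 days at the earliest, given QTc recovery. The ECG lists differ by one time point, with no statement of which applies. How many patients this will affect cannot be derived from the documents. No primary analysis is altered, so this is a should-fix on safety and consistency of dosing.

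**What to change.** The sponsor should amend 5.2.3, 5.2.4.3, the Table 2 QTc rows and 7.2.8 so that they state one rule:

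- whether, when and on what conditions quizartinib may be raised again after a Grade 2 and after a Grade 3 QTc event, with one waiting time for each;
- which rule applies when a QTc value fits both Table 2 QTc rows;
- whether 5.2.3 covers only escalation to a higher cohort level, with the reference in 7.2.8 B corrected to match;
- whether list A, list B or both apply to a re-escalated patient.

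The choice of clinical rule and of ECG list is for the sponsor. The cost is a wording amendment and, if the longer list is chosen, at most one more ECG per re-escalated patient.

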5.3 Duration of Therapy

In the absence of treatment delays due to adverse events, treatment may continue until one of the following criteria applies:

1. Clinically significant progressive disease, or
2. Grade 4 QTc prolongation (based on average of triplicate).
3. Intercurrent illness that prevents further administration of treatment, or
4. Patient request, or
5. General or specific changes in the patient's condition render the patient unacceptable for further treatment in the judgment of the investigator, or
6. Unacceptable toxicity that in the opinion of the investigator makes it unsafe to continue therapy. This includes patients with grade 4 non-hematological toxicity unless it reverses to grade ≤ 1 on or before 8 weeks of interrupting quizartinib and/or venetoclax.

5.3.1 It is planned that up to a total of 24 cycles of therapy will be administered for patients deriving benefit from this regimen. Continuation of therapy for patients completing 24 cycles of therapy may be considered on a case-by-case basis after discussion with the principal investigator.

5.3.2. All patients receiving at least one dose of either of the two drugs will be considered evaluable for toxicity.

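### Table 2 and section 5.3 item 6 disagree on the recovery grade needed to stay on treatment after a first Grade 4 non-hematologic drug-related toxicity

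*Combined protocol and SAP*

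**What the plan says.** Table 2 (section 5.2.2) covers drug-related non-hematologic events that the investigator considers clinically significant. For a first Grade 4 event it gives two routes back to treatment:

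- Early recovery: "Resume venetoclax and/or quizartinib at prior dose if recovery to ≤ Grade 1 or baseline occurs within 14 days".
- Slower recovery: "If toxicity persists for 15-28 days, hold therapy and resume at ONE dose level below current dose for venetoclax OR quizartinib OR both", by attribution, and "ONLY after recovery of toxicity to ≤ Grade 2".

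For a second Grade 4 event the default is "Stop venetoclax and quizartinib and discontinue patient". There is an exception for patients with clinical benefit or response: "we will consider continuation if toxicities resolve to ≤ grade 1 within 28 days", with dose adjustment and after consultation with the PI and the sponsor.

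Section 5.3 says that "treatment may continue until one of the following criteria applies" and then lists the criteria. Item 6 is unacceptable toxicity in the investigator's judgement, and it continues: "This includes patients with grade 4 non-hematological toxicity unless it reverses to grade ≤ 1 on or before 8 weeks of interrupting quizartinib" and/or venetoclax. It is not limited to drug-related events, does not separate first from second events, and has no exception for return to baseline.

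Grade 4 QTc prolongation has its own row in Table 2 and its own item in section 5.3, and is not part of this point.

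**The concern.** Both places decide whether a patient with a Grade 4 toxicity stays on treatment, but they use different recovery grades. Table 2 accepts Grade 2 for the reduced-dose restart, and accepts baseline, whatever its grade, for the early restart. Section 5.3 accepts only Grade 1 or lower. A clinician who follows Table 2 exactly can re-expose a patient who later meets a stopping criterion for the same event.

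This matters first for patient safety and for consistent management of severe toxicity. It also matters for conduct: section 9.3 lists departures from interruption, reduction and discontinuation criteria as a class of violation or deviation, so following one section could be recorded as breaching the other. The count of toxicity discontinuations may also depend on which section was applied.

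**Working it through.** The plan gives no figure to reproduce, so the check sets the two rules side by side. Days are counted from drug interruption, assumed to coincide with the onset of the event. Eight weeks = 8 × 7 = 56 days.

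| Course of a Grade 4 non-hematologic drug-related event | Table 2 | Section 5.3 item 6 | Result |
|---|---|---|---|
| 1. First event, Grade ≤1 within 14 days | Restart at prior dose | Criterion not met | Agree |
| 2. First event, Grade ≤1 reached on days 15-28 | Restart one level lower | Criterion not met | Agree |
| 3. First event, Grade 2 reached on days 15-28 and still Grade 2 at Day 56 | Restart one level lower | Criterion met at Day 56 | Conflict |
| 4. First event, back to a Grade 2 baseline within 14 days and still Grade 2 at Day 56 | Restart at prior dose | Criterion met at Day 56 | Conflict |
| 5. First event, Grade ≤1 reached on days 29-56 | No outcome stated | Criterion not met | Gap |
| 6. Second event, Grade ≤1 reached on days 29-56 | Discontinue | Criterion not met | Not cross-referenced |

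**Case 3 in numbers.** The toxicity reaches Grade 2 on Day 20 and stays there. Table 2 permits a restart from about Day 20. The exception in section 5.3 fails at Day 56. If the restart is immediate and dosing is uninterrupted, re-exposure before the criterion applies is 56 − 20 = 36 days, longer than one 28-day cycle. Across the Table 2 bracket, a restart on Day 15 gives 56 − 15 = 41 days and one on Day 28 gives 56 − 28 = 28 days. If the toxicity instead improves to Grade 1 by Day 56, the criterion is never met and the conflict does not arise.

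**Case 4.** An abnormal baseline is foreseeable, because inclusion criterion 5 admits raised bilirubin and transaminases attributed to leukemia. The documents do not say how many patients would start at Grade 2 for a given toxicity.

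**Does other text settle it?**

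- The note after Table 2 calls its rules guidance that discussion with the PI may supplement. It sets no order between sections.
- Section 5.2.4.4 allows other modifications after PI discussion, but does not address the Grade 4 recovery grade or waive section 5.3.
- Section 9.1.3 repeats unacceptable toxicity as a required reason to discontinue, without a grade or time limit.

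None of these says which recovery grade applies.

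**The case against.** The strongest defence is that the sections do different jobs. Table 2 governs dose and restart; section 5.3 is an outer limit that permits continuation and orders no restart. On Day 20 the instructions are not opposed, because section 5.3 is not tested until week 8, and the text does not say whether its clock keeps running after a restart. Item 6 also rests on the investigator's judgement, and section 5.3 opens by setting aside delays caused by adverse events. These points soften the conflict but do not remove it. Item 6 is itself about interruption for toxicity, and its second sentence places unresolved Grade 4 events in the stopping category.

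The defence does defeat several stronger readings that a reader might infer:

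- *The sections give opposite instructions after any Grade 4 toxicity.* They agree in cases 1 and 2.
- *Table 2 is stricter on time by a factor of two (28 against 56 days).* The limits govern different decisions. In Table 2, 28 days closes a dose-reduction bracket or conditions a second-event exception; in section 5.3, 8 weeks is an outer stopping limit.
- *A first event recovering in week 6 is barred from restarting.* Table 2 is silent, which is not a prohibition. Section 5.1.1.2 allows cycle delays for recovery, with extra conditions only beyond 8 weeks, and section 5.2.4.4 allows other modifications. They partly cover case 5.
- *The second-event rule contradicts section 5.3.* An earlier stop can sit inside a permissive outer limit without breaching it.
- *Nearly all such events in cycle 1 are DLTs.* No figure supports this, and section 3.4 exempts several kinds of Grade 4 event, including fatigue, anorexia, and raised amylase or lipase without clinical pancreatitis.

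**Conclusion.** The inconsistency is real but narrow. It concerns the recovery grade (Grade 2 or baseline against Grade 1) after a first Grade 4 non-hematologic event in the overlap of the two rules, that is, a drug-related and clinically significant event. It appears when the toxicity settles at Grade 2 and stays there to week 8. In that case Table 2 permits re-exposure for about 28 to 41 days before section 5.3 applies. This assumes that the 8-week clock runs from the interruption, is not reset by the restart, and that dosing resumes at once and continues.

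The absence of a stated outcome in Table 2 for a first event recovering between Day 29 and week 8, and of a cross-reference between its second-event rule and the 8-week limit, are secondary drafting gaps.

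A reader might also infer an effect on the trial's conclusions. The documents do not establish one. A DLT counts when it occurs, so the restart rule does not undo it. Section 11.3 includes every treated patient and counts those who drop out before completing all cycles as failures, but it does not say whether withdrawal for toxicity is a dropout. No frequency is available for the pattern, so any effect on the CRc rate or the discontinuation count cannot be sized.

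**What to change.** Reconcile the first-event Grade 4 row of Table 2 with section 5.3 item 6, so that both use the same recovery grade, the same treatment of a baseline above Grade 1 and the same maximum interruption. Alternatively, state which section governs. In either case:

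- State the outcome for a first event that recovers after Day 28.
- Cross-reference the second-event rule to the 8-week limit.
- State whether the 8-week clock continues after a restart.

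The grade and time limits are for the sponsor to choose. Aligning section 9.1.3 is optional, since it contains no conflicting threshold.

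The cost is a wording amendment to sections 5.2.2 and 5.3, with no added procedures, visits or patients.
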